3.1.1.4. Adverse Events

AEs will be assessed from the time of informed consent through and including Visit 3. AEs will be categorized according to MedDRA terms. Missing AE start dates will be imputed following the Pfizer data standard rules as described in [Section 5.3](#).

A 3-tier approach will be used to summarize AEs. Under this approach, AEs are classified into 1 of 3 tiers. Different analyses will be performed for different tiers (refer to [Section 5.2.1](#)).

- Tier 1 events are prespecified events of clinical importance and are identified in a list in the product’s safety review plan; there is no Tier 1 event identified for BNT162b2 at this stage.
- Tier 2 events are those that are not Tier 1 but are considered “relatively common”; a MedDRA preferred term is defined as a Tier 2 event if there are at least 1% of participants in at least 1 vaccine group reporting the event.
- Tier 3 events are those that are neither Tier 1 nor Tier 2 events.

The primary safety endpoint “AEs within 1 month after each vaccination” and other AE endpoints will be summarized by system organ class and preferred term.

These primary endpoints will be supported by summaries and/or listings of related AEs, severe AEs, immediate AEs (within the first 30 minutes after each vaccination), and AESIs (defined in Section 8.3.8 of the protocol: confirmed myocarditis or pericarditis, confirmed COVID-19 diagnosis or positive SARS-CoV-2 test result by NAAT or rapid antigen test).

3.1.1.5. Serious Adverse Events

SAEs will also be collected from the time of informed consent through and including Visit 3. SAEs will be categorized according to MedDRA terms.

The safety endpoint “SAEs from the first vaccination up to 1 month after the last vaccination” will be summarized by system organ class and preferred term. Additionally, SAEs will be listed.

3.1.2. Primary Immunogenicity Endpoints

- BNT162b2 immunogenicity: Full-length S-binding IgG levels 1 month after vaccination with BNT162b2 (the vaccination is at Visit 1 in the coadministration group and at Visit 2 in the separate-administration group).
- SIIV immunogenicity: Strain-specific HAI titers (or H3N2-neutralizing antibody titers if H3N2-HAI titers cannot be obtained) 1 month after vaccination with SIIV (the vaccination is at Visit 1 in the coadministration group and in the separate-administration group).

3.2. Secondary Endpoints

3.2.1. Secondary Immunogenicity Endpoints

- BNT162b2 immunogenicity:
 - a. Full-length S-binding IgG levels from before vaccination to 1 month after vaccination with BNT162b2.
 - b. SARS-CoV-2 neutralizing titers (for a subset of approximately 200 participants) from before vaccination to 1 month after vaccination with BNT162b2.
- SIV immunogenicity: Strain-specific HAI titers (or H3N2-neutralizing antibody titers if H3N2-HAI titers cannot be obtained) from before vaccination to 1 month after vaccination with SIV.

3.3. Other Endpoints

3.3.1. Exploratory Immunogenicity Endpoints

- SIV immunogenicity: Strain-specific HAI titers (or H3N2-neutralizing antibody titers if H3N2-HAI titers cannot be obtained) before vaccination and 1 month after vaccination with SIV.

3.4. Baseline Variables

Measurements or samples collected prior to the first vaccination are considered the baseline data for the assessments.

3.4.1. Demographics, Medical History, and Physical Examination

The demographic variables will be collected including date of birth, sex (male or female), race (Black/African American, American Indian or Alaskan native, Asian, Native Hawaiian or other Pacific Islander, White, multiracial, and not reported), racial designation, and ethnicity (Hispanic/Latino, non-Hispanic/non-Latino, and not reported). In cases where more than 1 category is selected for race, the participant would be counted under the category “multiracial” for analysis.

Age at the time of vaccination (in years) will be derived based on the participant’s birthday. For example, if the vaccination day is 1 day before the participant’s 50th birthday, the participant is considered to be 49 years old.

Medical history will be collected and categorized according to the current version (at the time of reporting) of MedDRA.

If the clinical assessment indicates that a physical examination is necessary to comprehensively evaluate the participant at Visit 1, a physical examination will be performed and any findings will be recorded in the source documents and, if clinically significant, the findings will be recorded on the medical history CRF.

3.4.2. E-Diary Transmission

An e-diary will be considered transmitted if any data for the local reactions, systemic events, or use of antipyretic medication are present for any day. If all data are missing for all the items on the e-diary for all 7 days after vaccination, the e-diary will be considered not transmitted.

3.4.3. Prior/Concomitant Vaccines and Concomitant Medications

The following concomitant medications and vaccinations will be recorded in the CRF:

- All vaccinations received from 28 days prior to study enrollment through Visit 3.
- Prohibited medications listed in the protocol, Section 6.8.1, will be recorded to include start and stop dates, name of the medication, dose, unit, route, and frequency.

Prior and concomitant vaccines and concomitant medications will be coded using the WHO Drug Dictionary.

3.5. Safety Endpoints

Local reactions, systemic events, AEs, and SAEs have been described above in the Primary Safety Endpoints section ([Section 3.1.1](#)).

4. ANALYSIS SETS (POPULATIONS FOR ANALYSIS)

Analysis populations are defined for the statistical analysis of safety and immunogenicity results in the table below. Data for all participants will be assessed to determine if participants meet the criteria for inclusion in each analysis population prior to unblinding and releasing the database, and classifications will be documented per standard operating procedures.

Population	Description
Enrolled	All participants who have a signed ICD.
Randomized	All participants who are assigned a randomization number in the IRT system.
Evaluable BNT162b2 immunogenicity	All eligible randomized participants who receive all vaccinations at Visit 1 as randomized (coadministration group) or receive all vaccinations at Visit 1 and Visit 2 as randomized (separate-administration group), have at least 1 valid and determinate full-length S-binding IgG or SARS-CoV-2 neutralizing titer result from the blood sample collected within the predefined window (within 28-42 days after receipt of BNT162b2) at Visit 2 (coadministration group) or at Visit 3 (separate-administration group), have no reported COVID-19 or new SARS-CoV-2 infection after Visit 1 and through 1 month after BNT162b2 vaccination (Visit 2 for the coadministration group and Visit 3 for the separate-administration group), and have no other important protocol deviations as determined by the clinician.
Evaluable SIIV immunogenicity	All eligible randomized participants who receive all vaccinations at Visit 1 as randomized, have at least 1 valid and determinate HAI titer or H3N2-neutralizing antibody titer result from the blood sample collected within the predefined window at Visit 2 (within 28-42 days after receipt of SIIV), and have no other important protocol deviations as determined by the clinician.
All-available immunogenicity	All randomized participants who have at least 1 valid and determinate immunogenicity result after receiving study intervention.
Safety	All participants who receive any of the study intervention.

Important protocol deviations will be determined by the medical monitor. An important protocol deviation is a protocol deviation that, in the opinion of the sponsor's clinician, would materially affect assessment of immunogenicity, eg, participant receipt of a prohibited vaccine or medication that might affect immune response or a medication error with suspected decrease in potency of the vaccine. The sponsor's medical monitor will identify those participants with important protocol deviations that result in exclusion from analysis populations before any unblinded analysis is carried out.

For all the immunogenicity endpoints, the analysis will be based on the relevant evaluable immunogenicity population. An additional analysis may be performed based on the all-available immunogenicity population if there is a $\geq 10\%$ difference in sample size between the all-available immunogenicity population and the evaluable immunogenicity population. Participants will be summarized according to the vaccine group to which they were randomized. Missing serology data will not be imputed.

The safety analyses are based on the safety population. Participants will be summarized by vaccine group according to the study intervention they actually receive. Missing reactogenicity e-diary data will not be imputed; missing AE start dates will be handled according to the Pfizer safety rules.

5. GENERAL METHODOLOGY AND CONVENTIONS

Methodology for statistical analyses of the data collected in this study is described here. The SAP may modify what is outlined in the protocol where appropriate; however, any major modifications of the primary endpoint definitions or their analyses will also be reflected in a protocol amendment.

The majority of sponsor/Pfizer staff will be blinded to study intervention allocation until the analysis at the completion of the study. All laboratory testing personnel performing serology assays will remain blinded to the study intervention assigned/received throughout the study. Further details can be found in the protocol, Section 6.3. The timing for statistical analysis is specified in [Section 7.2](#).

5.1. Hypotheses and Decision Rules

5.1.1. Immunogenicity Hypothesis

The primary immunogenicity objective on immune response elicited by BNT162b2 will be evaluated by the following hypothesis (H_{01}):

$$H_{01}: \ln(\mu_A) - \ln(\mu_B) \leq \ln(0.67)$$

where $\ln(0.67)$ corresponds to a 1.5-fold margin for noninferiority, and $\ln(\mu_A)$ and $\ln(\mu_B)$ are the natural log of the geometric mean of full-length S-binding IgG levels 1 month after vaccination with BNT162b2 for the coadministration group and the separate-administration group, respectively. Noninferiority will be declared if the lower limit of the 2-sided 95% CI for the GMR (coadministration group to separate-administration group) is >0.67 .

The primary immunogenicity objective on immune response elicited by SIIV will be evaluated by the following hypothesis (H_{02}) for each of the influenza strains:

$$H_{02}: \ln(\mu_C) - \ln(\mu_D) \leq \ln(0.67)$$

where $\ln(0.67)$ corresponds to a 1.5-fold margin for noninferiority, and $\ln(\mu_C)$ and $\ln(\mu_D)$ are the natural log of the geometric mean of the strain-specific HAI titers (or H3N2-neutralizing antibody titers if H3N2-HAI titers cannot be obtained) 1 month after vaccination with SIIV for the coadministration group and the separate-administration group, respectively. Noninferiority will be declared for an influenza strain if the lower limit of the 2-sided 95% CI for the GMR (coadministration group to separate-administration group) is >0.67 . The primary SIIV immunogenicity objective of the study will be achieved if the noninferiority is met for each of the influenza strains.

5.1.2. Multiplicity Considerations

For the primary immunogenicity assessment of noninferiority of coadministration of BNT162b2 and SIIV to administration of SIIV followed by BNT162b2 1 month later, each of the hypotheses described above in [Section 5.1.1](#) (the hypothesis based on the full-length S-binding IgG levels elicited by BNT162b2 and the hypotheses based on strain-specific HAI titers elicited by the influenza strains in SIIV) will be tested at a 1-sided alpha level of 0.025.

The primary immunogenicity objectives of the study will be achieved if noninferiority of coadministration to separate administration is met for BNT162b2 (full-length S-binding IgG levels) and for each of the influenza strains in SIIV (strain-specific HAI titers). Therefore, the type I error rate for the immunogenicity assessments is well controlled.

5.2. General Methods

Unless stated otherwise, “vaccine group” in this document refers to the coadministration group receiving BNT162b2 and SIIV at the same visit or the separate-administration group receiving SIIV followed by BNT162b2 1 month later.

CI for all endpoints in the statistical analysis will be presented as 2-sided at the 95% level unless specified otherwise.

5.2.1. Analyses for Binary Endpoints

Descriptive statistics for categorical variables (eg, proportions) are the percentage (%), the numerator (n) and the denominator (N) used in the percentage calculation, and the 95% CI where applicable.

The exact 95% CI for binary endpoints for each group will be computed using the F distribution (Clopper-Pearson).¹ The 95% CI for the between-group difference for binary endpoints will be calculated using the Miettinen and Nurminen² method.

3-Tier Approach for AE Summary

The 3-tier approach will be used to summarize AEs. For both Tier 1 (if any are identified during the study) and Tier 2 events, a 95% CI for the between-group difference in proportions will be calculated based on the Miettinen and Nurminen² method. In addition, for Tier 1 events (if any), the asymptotic p-values will also be presented for the difference in proportions, based on the same test statistic and under the assumption that the test statistic is asymptotically normally distributed. For Tier 3 events, counts and percentages for each vaccine group will be provided.

5.2.2. Analyses for Continuous Endpoints

Unless otherwise stated, descriptive statistics for continuous variables are n, mean, median, standard deviation, minimum, and maximum.

5.2.2.1. Geometric Mean Ratios

Model-Based

As the primary approach (only for primary endpoints), the GMRs and associated 95% CIs will be calculated by exponentiating the difference in LS means of the 2 vaccine groups and the corresponding CIs based on analysis of logarithmically transformed assay results using a linear regression model that includes vaccine group, age group, and corresponding baseline assay results as factors.

Unadjusted

The GMRs will be calculated as the difference in the means of logarithmically transformed assay results between 2 vaccine groups and exponentiating the difference. The associated 2-sided 95% CIs will be obtained by calculating CIs using Student's t distribution for the mean difference of the logarithmically transformed assay results and exponentiating the confidence limits.

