10.8. Appendix 8: Protocol Amendment History

The Protocol Amendment Summary of Changes Table for the current amendment is located directly before the table of contents (TOC). The protocol amendment summary of changes tables for past amendment(s) can be found below:

Amendment 1 (22 December 2021)

Overall Rationale for the Amendment: The BNT162b2 booster rollout in southern hemisphere countries will significantly reduce the pool of potential study participants ≥ 65 years of age because the majority will be due to receive their BNT162b2 booster prior to study start. The age eligibility of this study has been modified to include a younger age group who will be eligible for the booster vaccination during the planned study recruitment period. **CCI**

Section # and Name	Description of Change	Brief Rationale
Study title, Section 1.1 (Synopsis), Section 2.1 (Study Rationale), Section 4.1 (Overall Design), Section 5.1 (Inclusion Criteria)	Updated age eligibility to include adults 18 through 64 years of age (stratified by age group [18-49 years and 50-64 years] and the removed ≥ 65 -year age group.	Updated to mitigate risk to the achieving recruitment target.
Section 9 (Statistical Considerations)	Updated sample size calculations with new assumptions on assay SDs in Table 5. An additional reference (19) was added for assay SDs of HAI endpoints based on Afluria Quad.	Modified to reflect younger age group and comparator SIIV.
	Added a linear regression model to calculate GMR for the primary immunogenicity endpoints.	Updated to accommodate added stratifications (age and timing of the second dose of BNT162b2 prior to Visit 1) in the randomization of the study design.
	Revised the names of immunogenicity populations.	Updated to match the wording of the objectives.

Section # and Name	Description of Change	Brief Rationale
Section 1.2 (Schema), Section 5.1 (Inclusion Criteria)	Updated eligibility criteria to include participants who have received their second dose of 30 µg BNT162b2 90 to 365 days before Visit 1 (Day 1).	Updated to accommodate potential shorter booster intervals because of emerging VOCs.

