3/ 20 Oct 2022	N/A	Implemented the changes made in the decision log (based on clinical and statistical consideration, refining the definition and analysis of evaluable BNT162b2 immunogenicity population).	
 Added, “have no reported COVID-19 or new SARS-CoV-2 infection after Visit 1 and through 1 month after the BNT162b2 vaccination (Visit 2 for the coadministration group and Visit 3 for the separate-administration group)” in the definition of the evaluable BNT162b2 immunogenicity population in Section 4. Replaced “evidence of SARS-CoV-2 infection” with “corresponding baseline assay results” from the primary analysis model in Sections 5.2.2.1, 6.1.2.1, and 6.1.2.2. In Section 6.4 Subset Analyses, replaced “without evidence of SARS-CoV-2 infection through 1 month after BNT162b2 vaccination” with “baseline SARS-CoV-2 status (based on N-binding antibody results at Visit 1 before vaccination and medical history of SARS-CoV-2).”
		Clarification	In Section 6.2.1.1.1 , added clarification that “before vaccination” refers to Visit 1 for the coadministration group and Visit 2 for the separate-administration group.
		Clarified the supplemental analyses	Moved the designation of “without evidence of infection” to newly added Section 6.1.2.1.2 (Supplemental Analysis).
		Timing from BNT162b2 is more clinically relevant to the BNT endpoint.	In Section 6.5.1.1 , revised “timing of the third dose of BNT162b2 prior to Visit 1” to “timing of the third dose of BNT162b2 prior to BNT162b2 vaccination received during the study.”

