2.2. Study Design

This is a Phase 3, multicenter, randomized, 2-arm parallel, observer-blind study in adults 18 through 64 years of age to assess the safety and immunogenicity of a booster dose of BNT162b2 and SIIV given together compared to the vaccines given 1 month apart. Approximately 1126 participants will be randomized at a ratio of 1:1 into the coadministration group and the separate-administration group stratified by age group (18-49 years and 50-64 years) and by history of positive SARS-CoV-2 test by NAAT or rapid antigen test prior to randomization (with and without prior history of SARS-CoV-2). Assuming a 20% nonevaluable rate, there will be approximately 900 evaluable participants. Each participant will participate in the study for approximately 2 months with 3 scheduled visits.

Local reactions (redness, swelling, and pain at the injection site) occurring at the BNT162b2 or saline injection site within 7 days and systemic events (fever, headache, fatigue/tiredness, chills, vomiting, diarrhea, new or worsening muscle pain, and new or worsening joint pain) occurring within 7 days after each vaccination (Visit 1 and Visit 2) will be prompted for and collected daily by the participant in an e-diary device or application. Use of antipyretic/pain medications will also be prompted for and collected daily in the reactogenicity e-diary for 7 days after each vaccination.

AEs and SAEs will be collected from the signing of informed consent through Visit 3 (approximately 1 month after Vaccination 2).

To assess immunogenicity, approximately 30 mL of blood will be collected from all participants at 3 study visits: at Visit 1 (prior to Vaccination 1); at Visit 2 (prior to Vaccination 2); and at Visit 3 (1 month after Visit 2).

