6.1.2.1.1. Main Analyses

- Estimands: GMR of full-length S-binding IgG levels 1 month after vaccination with BNT162b2 (at Visit 1) in the coadministration group to the IgG levels 1 month after vaccination with BNT162b2 (at Visit 2) in the separate-administration group ([Section 2.1](#)).
- Analysis set: Evaluable BNT162b2 immunogenicity population, all-available immunogenicity population (as applicable) ([Section 4](#)).
- Analysis time point: 1 Month after vaccination with BNT162b2.
- Analysis methodology: The GMR and the associated 2-sided 95% CIs will be calculated using the statistical methods described in [Section 5.2.2.1](#). Noninferiority will be declared if the lower bound of the 2-sided 95% CI for the GMR is greater than 0.67 ([Section 5.1.1](#)).
- Intercurrent events and missing data: Serology data deemed unevaluable because of noncompliance with the key protocol criteria will be excluded. Missing data will not be imputed.
- Reporting results: The adjusted GMR and 2-sided 95% CI will be calculated based on the primary approach using a linear regression model that includes vaccine group, age group, and baseline (Visit 1 for the coadministration group and Visit 2 for the separate-administration group) full-length S-binding IgG levels as factors. The unadjusted GMR and the associated 2-sided 95% CI will also be provided.

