6.1.2.1.2. Supplemental Analyses

Supplemental analysis will be performed in participants without evidence of SARS-CoV-2 infection through 1 month after BNT162b2 vaccination. The unadjusted GMR and the associated 2-sided 95% CI will be provided. The designation of “without evidence of SARS-CoV-2 infection through 1 month after BNT162b2 vaccination” is given to participants who have no serological or virological evidence (prior to the 1-month post-BNT162b2 vaccination blood sample collection) of SARS-CoV-2 infection (ie, N-binding antibody negative before study vaccination and at the 1-month post-BNT162b2 vaccination visit, and no reported SARS-CoV-2 infection or COVID-19 through the 1-month post-BNT162b2 vaccination blood sample collection) and have no medical history of SARS-CoV-2.

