6.1.2.2.1. Main Analyses

- Estimands: GMR of the strain-specific HAI (or H3N2-neutralizing antibody) titers 1 month after vaccination with SIV in the coadministration group to the corresponding HAI (or H3N2-neutralizing antibody) titers in the separate-administration group ([Section 2.1](#)).
- Analysis set: Evaluable SIV immunogenicity population, all-available immunogenicity population (as applicable) ([Section 4](#)).
- Analysis time point: 1 Month after vaccination with SIV.
- Analysis methodology: For each influenza strain, the GMRs and the associated 2-sided 95% CIs will be calculated using the statistical methods described in [Section 5.2.2.1](#). Noninferiority for a strain will be declared if the lower bound of the 2-sided 95% CI for the GMR is greater than 0.67. The primary SIV immunogenicity objective of the study will be achieved if the noninferiority is met for each of the influenza strains ([Section 5.1.1](#)).
- Intercurrent events and missing data: Serology data deemed unevaluable because of noncompliance with the key protocol criteria will be excluded. Missing data will not be imputed.
- Reporting results: The adjusted GMR and 2-sided 95% CI will be calculated based on the primary approach using a linear regression model that includes vaccine group, age group, and corresponding baseline strain-specific HAI (or H3N2-neutralizing antibody) titers as factors. The unadjusted GMR and the associated 2-sided 95% CI will also be provided.

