6.4. Subset Analyses

Subgroup analyses based on age group, sex, race (if appropriate), and racial designation, as well as baseline SARS-CoV-2 status (based on N-binding antibody results at Visit 1 before vaccination and medical history of SARS-CoV-2), will be performed on all primary safety and immunogenicity endpoints (as supplemental analyses).

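### The SAP's primary GMR model leaves out one of the two randomisation strata, history of a positive SARS-CoV-2 test

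*SAP*

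**What the plan says.** SAP 2.2 and Protocol 4.1 stratify the 1:1 randomisation by age group (18-49, 50-64) and "by history of positive SARS-CoV-2 test by NAAT or rapid antigen test prior to randomization".

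SAP 5.2.2.1 defines the primary approach as a "linear regression model that includes vaccine group, age group, and corresponding baseline assay results as factors". The endpoint sections repeat this. For IgG (SAP 6.1.2.1.1) the terms are "vaccine group, age group, and baseline (Visit 1 for the coadministration group and Visit 2 for the separate-administration group") IgG. For influenza (SAP 6.1.2.2.1) they are "vaccine group, age group, and corresponding baseline strain-specific HAI (or H3N2-neutralizing antibody) titers as factors". Neither contains the history stratum.

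Two change logs bear on purpose only, since they describe superseded text. Protocol 10.8 explains the introduction of the regression model as "Updated to accommodate added stratifications (age and timing of the second dose of BNT162b2 prior to Visit 1) in the randomization". SAP section 1 attributes the version 3 change, in which the baseline assay result replaced infection evidence, to decisions "based on clinical and statistical consideration, refining the definition and analysis of evaluable BNT162b2 immunogenicity population". It does not mention the stratum.

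Related information is used elsewhere. The supplemental IgG analysis (SAP 6.1.2.1.2) requires that participants be free of infection evidence "and have no medical history of SARS-CoV-2", and the subgroup analyses (SAP 6.4) use "baseline SARS-CoV-2 status (based on N-binding antibody results at Visit 1 before vaccination and medical history of SARS-CoV-2").

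**The concern.** A factor used to stratify randomisation is balanced by design. If it also predicts the outcome, a model without it leaves its variance in the residual. The treatment estimate is then about as precise as with the term, but its reported standard error is too large. The interval does not reflect how the trial was randomised, and the noninferiority test becomes mildly conservative.

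Prior infection could plausibly affect the IgG response to a booster. The question is whether it does so beyond what baseline IgG already captures.

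A smaller second point applies to IgG only. SAP section 4 excludes participants with a new infection up to Visit 2 in the coadministration group but up to Visit 3 in the separate-administration group. If infection risk depends on history, the evaluable arms can drift apart on the factor that randomisation balanced, and a history term would adjust for that.

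**Working it through.** **The plan's own figures (Protocol 9.5, Table 5).** At GMR 0.9, margin 0.67, SD 1.05 and 450 per group, SE = 1.05 × √(2/450) = 0.0700. The distance to the margin is ln(0.9) − ln(0.67) = 0.2951. Power is Φ(0.2951/0.0700 − 1.96) = Φ(2.26) = 98.8%, as stated. The product over the five endpoints is 90.7%, as stated. For the sample size, 450/0.8 = 562.5, rounded up to 563 per group, or 1126.

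**Assumed inputs.** The documents do not give these: history share p = 30-50%; history shifting baseline ln IgG by s = 0.5-1.0 SD; residual SD 0.9; effect of history beyond baseline d = 0, 0.3 or 0.6 ln units.

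**Width of the reported IgG interval.** The share of history variance explained by baseline is R² = s²p(1−p)/(1 + s²p(1−p)). The ratio of the interval width without the stratum to the width with it is √(1 + d²p(1−p)(1−R²)/0.81).

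- d = 0.6, p = 0.5, s = 0.5: R² = 0.0625/1.0625 = 0.059; √(1 + 0.36 × 0.25 × 0.941/0.81) = 1.051.
- d = 0.6, p = 0.3, s = 1.0: R² = 0.21/1.21 = 0.174; √(1 + 0.36 × 0.21 × 0.826/0.81) = 1.038.

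| Effect beyond baseline (ln units) | Widening, formula | Mean reported SE without / with stratum, simulated |
|---|---|---|
| 0 | 0% | 0.0600-0.0601 / 0.0600-0.0601 |
| 0.3 | 0.96-1.30% | 0.0606-0.0608 / 0.0600 |
| 0.6 | 3.79-5.10% | 0.0623-0.0631 / 0.0600 |

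The simulation used 900 participants, permuted blocks of 4 (assumed) within the four strata, baseline slope 0.5 and 2500 runs per cell.

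**Lower confidence limit at GMR 0.9, d = 0.6.** With the stratum: 0.9 × exp(−1.9626 × 0.0600) = 0.800. Without it: 0.9 × exp(−1.9626 × 0.0623 to 0.0631) = 0.796 to 0.795.

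**Power at residual SD 0.9.** Φ(0.2951/0.0600 − 1.9626) = 99.84%. With a reported interval 5% wider: Φ(4.919 − 1.05 × 1.9626) = 99.79%.

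**Type I error.** At a true GMR of 0.67 with d = 0.6 and s = 0.5 (6000 runs, Monte Carlo SE 0.2%), the one-sided error is 2.0-2.1% without the stratum and 2.5-2.6% with it, against a nominal 2.5%. The analytic value agrees: Φ(−1.96 × 1.051) = 2.0%. The empirical SD of the log GMR hardly changes (0.0585-0.0612 without, 0.0584-0.0608 with). The true variability is therefore unaffected; only the reported SE is too large.

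**HAI.** With an assumed effect of 0-0.1 and the Table 5 SDs of 1.05-1.16, the widening is at most √(1 + 0.01 × 0.25/1.1025) − 1 = 0.11%.

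**Unequal exclusion windows (IgG, illustrative).** Take p = 0.5 and assumed monthly infection risks of 15% without history and 5% with it. After one month the history share is 0.95/(0.95 + 0.85) = 52.8%. After two months it is 0.9025/(0.9025 + 0.7225) = 55.5%. The GMR factor at d = 0.6 is exp(−0.6 × 0.0276) = 0.984. With risks of 15% and 2%, the shares are 53.5% and 57.1% and the factor is 0.979. Equal risks give 1.000. The shift reverses if the history effect is negative. Baseline IgG in the model would absorb part of it. In a separate simulation (p = 0.3, risks 15% and 3%, d = 0.8, true GMR 0.67), the estimate was 0.656 without the term and 0.670 with it.

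**The case against.** The strongest reply is that this is a choice between two valid models with no practical consequence. Type I error is not inflated, power stays above 99% at the assumed residual SD, and the lower limit moves by about 0.005 when it is some 0.13 above the margin. For four of the five Table 5 endpoints the gain is near zero. Baseline IgG is a continuous measure that can also reflect untested infection, and version 3 adopted it deliberately. The subgroup and supplemental analyses use infection history, and SAP 6.5.1.1 summarises baseline infection status by group in the evaluable populations, so an imbalance would be visible.

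Much of this stands, and it is why the point is minor. It does not supply a reason for leaving out the stratum, and none of those analyses adjusts the primary GMR for it.

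The residual SD of 0.9 is an assumption, and Table 5 uses 1.05 for IgG. With 1.05 the widening falls to 0.7-1.0% (d = 0.3) and 2.8-3.8% (d = 0.6). Nothing in the documents supports an effect as large as 0.6.

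The protocol (9.3.1.2.1, 9.3.2) and the SAP state different primary models. If the protocol's infection-evidence factor, defined as in SAP 6.1.2.1.2, were retained, it would largely contain history, and a separate term would not be wanted. That affects how and when the change is made. It does not alter the fact that the SAP model as written omits the stratum.

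**Conclusion.** The concern holds at low severity. The SAP's primary model omits one of two randomisation strata without explanation. The cost is a reported IgG interval that is between 0% and about 5% too wide, depending on an effect of history beyond baseline IgG that the documents do not give. The error is in the conservative direction, and a noninferiority conclusion is unlikely to change. For HAI there is practically nothing to gain. The possible shift from unequal exclusion windows is 0-2.1% of the GMR at effects of 0.3-0.6 under the assumed infection risks, and its direction is unknown.

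The omission is certain from the text. The size of the benefit rests entirely on assumed inputs.

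**What to change.** In SAP 5.2.2.1 and 6.1.2.1.1, add history of a positive SARS-CoV-2 test, using the value entered at randomisation in the IRT system, as a factor in the primary IgG model. The HAI models in 6.1.2.2.1 can carry the same term for consistency. Specify this before unblinding.

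If the sponsor prefers to omit the term, state the reason and report the stratum-adjusted IgG GMR as a sensitivity analysis.

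When the protocol and SAP primary models are reconciled, carry one model into Protocol 9.3.1.2.1 and 9.3.2. Do not place history beside the infection-evidence factor, because the two overlap. Which visit supplies the IgG baseline is a separate matter.

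The cost is one model term. With 900 evaluable participants the residual degrees of freedom go from 896 to 895. If history predicts nothing, the interval widens by √(896/895) − 1, about 0.06%. No new data or participants are needed. Both documents require major changes to the primary analysis to be reflected in a protocol amendment; the amendment that reconciles the two models can cover this one.
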